1 STUDY OBJECTIVES

1.1 Primary Objective

The purpose of this study is to evaluate the safety, feasibility and outcome of administering three different statins at submaximal and maximal dose on eCD and dCD. We hypothesize that a pre-operative statin regimen is protective against eCD (12-25h post-CEA) and dCD (30d), and early (365d) mortality. In addition, maximal doses may be essential in achieving optimal neuroprotection against eCD and dCD, with statins that pass the blood-brain barrier achieving similar effects at lower doses due to enhanced entry into the brain. In order to test this, our primary objectives will be:

- 1) Determine whether patients on a pre-existing sub-maximal dose of one of three most commonly prescribed statins (simvastatin <40mg, atorvastatin <80mg, rosuvastatin <20mg) experience a higher incidence of eCD and dCD than those randomized to 218 doses of pre-operative statin supplementation to the maximal FDA approved dose (simvastatin 40 mg, atorvastatin 80 mg, rosuvastatin 20 mg).
- 2) Determine whether approximately 2-18 doses of maximal statin supplementation is sufficient by comparing whether patients randomized to receiving statin supplementation each individually experience a higher incidence of eCD and dCD than those patients on a pre-existing maximal dose of the three most common statins, and whether statins that pass the blood-brain barrier better correlate with reduced eCD and dCD.
- 3) Determine whether patients on no pre-existing statin regimen exhibit less eCD and dCD when randomized to 2-18 doses of pre-operative maximal dose of atorvastatin (80mg) compared to lower dose of atorvastatin (10mg).
- 4) Determine a dose-response relationship to these 3 statins by determining whether all patients at the time of surgery have less eCD and dCD if they are on: 1) simvastatin 40mg rather than on <40mg; 2) atorvastatin 80mg rather than on <80mg; and 3) rosuvastatin 20mg rather than on <20mg.

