Additional support for the study rationale comes from the previous study with a cohort of asymptomatic CEA patients and regardless of statin dose or type, where it was found that ~20% of patients' not on statins had cognitive dysfunction compared to 11% of patients on statins.(72) This statistic alone leads us to believe that while a higher dose may be "more neuroprotective," any statin therapy at all will be beneficial to a patient undergoing CEA, and should become standard of care. Although we have evidence to demonstrate the efficacy of statin neuroprotection in CEA, the aim of this study is to reconfirm this and indicate that statin use

should be a standard of care preoperatively. We do not have a dose response curve and are guessing that a high dose is most beneficial. The purpose of this study is to show that. In addition, patients in the first arm of the study who are already on the high dose will be maintained, so no risk there. Patients in the second arm of the study, having already been started on statins, will just maintain the original regimen deemed appropriate by their prescribing physician or a higher, maximal dose, which we hope to demonstrate will reduce the incidence of cognitive dysfunction. Regardless of the randomization, they will be on a dose considered to be suitable for them and we believe they will experience sufficient neuroprotection peri-operatively. As for the third arm of this study, while we would have liked to randomize patients not already on a statin, to placebo or maximal high dose of atorvastatin, we think that providing a low dose may be sufficient. There is no evidence of the most effective dose of atorvastatin or any statin to provide increased benefit. These patients not already on statin therapy, will have ~2 week preoperative statin period which will afford significantly greater protection than going into CEA without any statin therapy. As no patients in this study will be entirely without statin therapy, we feel the benefit of a statin in general (versus no statin) greatly outweighs the issue of optimal (versus sub-optimal) dose.

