4.2 Exclusion Criteria

- 1) Patient has underlying disease other than atherosclerosis (i.e. autoimmune disease, known active malignancy).

- 2) Patient has documented dementia or screens out based on abnormal Baseline MoCA (≤ 25) and AD8 (≥ 2).
- 3) Patient's life expectancy is < 12 months.
- 4) Patient has advanced renal failure (serum creatinine > 2.5 mg/dL)
- 5) Patient has evidence of severe congestive heart failure or has history of end-stage cardiovascular disease (e.g. CHF NYHA Class III or IV or unstable angina).
- 6) Patient has history of intolerance or allergic reaction to any statins (myotoxicity, hepatic dysfunction, rash, etc.) – unless they would be in the Observational Arm (Arm 1) and therefore will not be receiving any study drug.
- 7) Patient has received an investigational drug within 30 days.
- 8) Patient is pregnant or lactating.
- 9) Except those eligible for the Observational Arm who do not receive any study statin, patient who is currently taking any of the following which have been shown to interact with atorvastatin and/or simvastatin and/or rosuvastatin (as per current drug package inserts):
 - *Cyclosporine;
 - *HIV Protease Inhibitors/Antivirals (e.g. roatanavir or plus roatanavir, tipranavir, lopinavir, boceprevir, saquinavir, darunavir, fosamprenavir, nelfinavir, efavirenz/tenofobir, atazanavir, simeprevir);
 - *Hep C Protease Inhibitor/Antivirals (e.g. telaprevir);
 - *Antibiotics (i.e. cobicistat-containing products like Tybost, rifampin/rifampicin, clarithromycin, telithromycin, erythromycin);
 - *Anti-fungals (i.e. itraconazole, ketoconazole, posaconazole, voriconazole, fluconazole); *Gemfibrozil; Other Fenofibrates (e.g. Tricor, fibric acid);
 - *Niacin > 1 g/day or statins in combination with niacin (e.g. Vytorin, Simcor);
 - *Colchicine;
 - *Danazol;
 - *Calcium Channel Blockers: Diltiazem, Varapamil;
 - * Dronedarone;
 - *Amiodarone;
 - *Digoxin;
 - *Ranolazine;
 - *Nefazodone;
 - *Warfarin/Coumadin;
 - *Lomitapide;
 - *Grapefruit juice (subject must be willing to avoid grapefruit juice).

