7 SAFETY ASSESSMENTS

7.1 Clinical Risks

Patients will have clinical laboratory tests upon enrollment and a research coordinator or nurse will contact them 3 days after starting the study drug to verify the patient's complying with the statin regimen as well as to ask questions regarding their subjective experience of taking the study assigned statin regimen (if the CEA does not occur prior to day 3). If the CEA does happen prior to day 3, the Day of CEA Safety Questionnaire will verify compliance and ask about the subjects experience with the assigned statin regimen. Patients will be asked about a variety of symptoms associated, though rarely, with statin use. According to the FDA, the value of statins has been clearly established yet they also advise that statins,

including the ones which will be part of this study (i.e. simvastatin, atorvastatin and rosuvastatin) offer some rare, but potential risks to statin users:¹

- Hepatic toxicity (indicator symptoms: elevated liver enzymes, bleeding or jaundice)
- Muscle toxicity (indicators symptoms: myalgia and arthralgia)
- Increased glucose levels

In addition, from clinical practice, we also know that statins may produce some minor gastrointestinal discomfort; however, these are minor and mostly tolerated as the benefit of statins tends to outweigh the minor stomach upsets they may produce in some individuals.

Patients randomized to maximize their statin regimen or randomized into the atorvastatin 80mg group are the only patients we anticipate having any risk of side effects.

If a patient reports subjective experiences of side effects, their statin regimen will be modified at the discretion of the caring physician. Although the randomization of the patient is compromised, we will continue to evaluate that patient and proceed with intention to treat principles. If the laboratory values the morning of surgery present with elevations in CK or LFT, their statin regimen will be modified at the discretion of the caring physician.

Other Potential Study Procedure Risks:

- Some people may feel uncomfortable taking cognitive tests.
- Slight pain and/or temporary discoloration of the skin after blood draws.
- Unlikely, but potential breach of confidentiality

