9 STATISTICAL CONSIDERATIONS

9.1 General Design Issues

For all analyses, the primary outcome will be derived from changes in test scores between enrollment and the morning of surgery (baseline), Day 1 post CEA (12-25 h post-op) (eCD) and Day 30 +/- 5 days after CEA or Day of Post-Operative clinical visit (dCD). Neuropsychometric assessment at baseline, will allow screening for MCI and determining if there is a change in cognitive performance from recruitment to operative day due to statin alteration. The intention to treat principle will be used for all analyses. All of the analyses will be performed in two general ways. 1) Significant neurocognitive change for both CEA will be defined compared to an appropriate reference group frequency matched for age, education level, pIQ, and type of anesthetic or sedation. Significant eCD will be defined as performance: (1) $\geq 2SD$ worse than reference group in two or more cognitive domains or (2) $\geq 1.5SD$ worse than the reference group in all cognitive domains tested.

The following data will be kept for patients having CEA: demographic and risk factor variables (age, gender, race, a history of hypertension, diabetes, level of glycosylated hemoglobin, previous myocardial infarction, previous CEA, ApoE genotype, pre-morbid IQ, MCI), degree of carotid stenosis, all additional cerebrovascular workup (i.e. Intracranial MRA, SPECT scanning, angiography, etc.), previous surgeries/anesthetics, laboratory values, all standing medication names (statin usage), doses, and

durations, and all neurologic and neuropsychological scores. Data will also be kept on the results of the delirium screen and the post-operative pain scores.

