9.2.1 Treatment Assignment Procedures

The randomization design will be stratified by center, previous use of statin and in random blocks of 4 and 6. The randomization process will be supported by the Statistical Analysis Center (SAC) at the Mailman School of Public Health at Columbia University. SAC will provide a central secure web-based randomization data system. All trials supported by the SAC employ central randomization that takes place in real-time. In other words, the patient's treatment assignment is made at the moment of randomization, based on probabilities calculated according to the randomization scheme, and communicated to the recruiting site via a central source (i.e. a secure web site).

- Patients on maximum dose of one of the three statins will be maintained on that dose (ARM 1). This arm will contain 225 participants.

- Those patients on submaximal doses of the 3 study statins will be randomized to their current dose plus placebo or their current dose plus the additional milligrams necessary to bring to raise them to the maximal daily dose of simvastatin (40 mg) or atorvastatin (80 mg) or rosuvastatin (20 mg) depending on which statin they are already on, (ARM 2). There will be 337 participants maintained at their current dose and 338 raised to the maximum dose of their statins.
- If patients are statin naïve, then they will be randomized to either atorvastatin 10 mg or 80 mg daily (ARM 3). ARM 3 will have 50 participants in each arm.

The randomization will be performed automatically by the web-based data system. No one will have access to unblinded treatment information on a regular basis other than the packaging pharmacy. All handling of study medication will take place using blinded bottle codes. It is not expected that serious adverse events will require revelation of treatment assignment, but the study web site will provide for online unblinding in emergencies. Revelation of treatment assignment will be available only to authorized users, who will be required to provide a clinical justification for unblinding. Each case of unblinding will be addressed by study personnel to ensure access to unblinded treatment assignment information is limited, and that such incidents are limited to circumstances where it is necessary for the health of the patient.

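### Primary Objective 4 claims a dose-response but makes one maximal v below-maximal split per statin that pools non-randomised Arm 1 with randomised patients

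*Combined protocol and SAP*

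**What the plan says.** Objective 4 in Section 1.1 is to "Determine a dose-response relationship to these 3 statins by determining whether all patients at the time of surgery have less eCD and dCD". For each statin, the comparison is between patients on "simvastatin 40mg rather than on <40mg; 2) atorvastatin 80mg rather than on <80mg; and 3) rosuvastatin 20mg rather than on <20mg". The Precis repeats it. It is one of four primary objectives.

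Arm 1 is observational: patients already on a maximal dose stay on it. Section 9.2.1 says "This arm will contain 225 participants". It plans 338 Arm 2 patients raised to the maximum and 337 kept at their current dose, and 50 Arm 3 patients each on atorvastatin 80 mg and 10 mg.

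Arm 1 has different entry rules. In Section 4.2 the statin-intolerance exclusion applies "unless they would be in the Observational Arm (Arm 1) and therefore will not be receiving any study drug". Criterion 9, on interacting drugs, makes a similar exception.

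On analysis, Section 9.1 states: "The intention to treat principle will be used for all analyses". Section 9.5 repeats this. Section 9.2 names logistic regression on eCD for every aim, with a separate analysis of dCD. Section 9.1 adjusts for risk factors that differ between groups at p<0.10. No model, dose term, arm term or power figure is given for Objective 4.

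On purpose, Section 2.2 says: "We do not have a dose response curve and are guessing that a high dose is most beneficial". Section 2.1.5 also stresses the value of generating such a curve.

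**The concern.** Three features work against a causal or dose-response reading.

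- **Non-randomised patients load one side.** Arms 2 and 3 are each randomised about 1:1, so alone they give balanced groups. Arm 1 falls almost wholly on the maximal side. Its patients differ in why they were prescribed that dose, in eligibility, and in having taken it before enrolment rather than for 2 to 18 pre-operative doses. Objective 2 asks whether short supplementation matches a pre-existing maximal dose; Objective 4 merges those two groups as if that were settled.
- **Grouping follows the dose held at surgery.** Section 7.1 says that if a patient reports side effects, "their statin regimen will be modified at the discretion of the caring physician". Read literally, Objective 4 could move such a patient out of the assigned group.
- **There are only two levels per statin.** One contrast gives one difference, not a curve.

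At stake is a primary claim about dose that may partly reflect the prognosis of people already on a maximal dose. Secondary Objective 2 builds on differences found under Objectives 1-4, so any bias carries forward.

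**Working it through.** **Plan's own figure.** None is stated for Objective 4. The nearest is Objective 1: 338 v 337, power 0.8, alpha 0.05 (two-sided assumed), 46.7% minimum detectable reduction. No control rate is given. Solving the two-proportion formula for it returns 14.5%, which is close to the 11% to 16% eCD rates quoted for statin users in the background. I use 14.5% below.

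**Composition** (protocol's definition of maximal, statins pooled):
- Maximal: 225 + 338 + 50 = 613.
- Sub-maximal: 337 + 50 = 387.
- Arm 1 share of the maximal side: 225/613 = 36.7%.

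Per-statin numbers are not given. If each arm divides equally by statin (assumption), simvastatin and rosuvastatin each have 75 + 113 = 188 v 112. Atorvastatin, which takes all of Arm 3, has 75 + 113 + 50 = 238 v 112 + 50 = 162.

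**Apparent effect when dose does nothing.** Let Arm 1's underlying risk be r times that of the randomised patients (r is assumed). The pooled risk ratio is (388 + 225r)/613:
- r = 0.8: 568/613 = 0.93
- r = 0.67: 538.75/613 = 0.88
- r = 0.5: 500.5/613 = 0.82

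**False-positive rate, unadjusted.** With d = p1 − p0, s0 = √[p̄(1−p̄)(1/n1 + 1/n0)] and s1 = √[p1(1−p1)/n1 + p0(1−p0)/n0], the rejection probability is Φ((−1.96·s0 − d)/s1) + Φ((−1.96·s0 + d)/s1).

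Example, r = 0.5, pooled: p0 = 0.145; p1 = 0.145 × 0.816 = 0.1184; d = −0.0266; p̄ = 0.1287; s0 = 0.0217; s1 = 0.0222. The first term is Φ(−0.72) = 0.235 and the second is about 0.001, giving 0.24.

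| Assumed r | Pooled, 613 v 387 | Simvastatin or rosuvastatin, 188 v 112 | Atorvastatin, 238 v 162 |
|---|---|---|---|
| 1 (no difference) | 5% | 5% | 5% |
| 0.8 | 8% | 6% | 6% |
| 0.67 | 13% | 8% | 7% |
| 0.5 | 24% | 12% | 10% |

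The direction is not known. At r = 1.5 the pooled risk ratio is (388 + 337.5)/613 = 1.18, which would mask a benefit or suggest harm.

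**Shape.** Suppose sub-maximal atorvastatin patients are in equal thirds on 10, 20 and 40 mg, with 8% eCD on 80 mg. Illustrative rates of 16/16/16%, 20/16/12% and 32/8/8% all average 16%. A threshold, a graded response and an early plateau therefore give the same 16% v 8% contrast.

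**Price of leaving Arm 1 out.** At an assumed 16% control rate and 80% power, the minimum detectable reduction is 41.8% for 388 v 387, against 37.8% for 613 v 387.

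**The case against.** Several counter-arguments have force.

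- **Arm 1 is not entirely on the maximal side.** A reader might infer that it is. Sections 3 and 5.1 also put patients on simvastatin 20 mg plus amlodipine in Arm 1, and Objective 4's literal 40 mg cut places them below. Arm 2 patients on amlodipine, who can be raised only to 20 mg, fall there too. So 613 v 387 holds under the protocol's definition of maximal, not under the literal cut. This stands, and it adds misclassification rather than removing confounding.
- **The plan does not prescribe an as-treated analysis.** That reading is tempting, but for patients reporting side effects Section 7.1 goes on to commit to intention to treat. What stands is a conflict of wording: the objective groups by dose held at surgery, while Sections 7.1, 9.1 and 9.5 require assigned groups.
- **Adjustment is planned.** Section 9.1 records statin use, doses and durations, diabetes, ApoE and prior infarction. But adjustment depends on significance tests of balance and includes no term for randomised status. It need not remove differences in indication, eligibility or duration of use.
- **The intolerance exemption may be narrower than it looks.** Section 7.3 refuses anyone with side effects at the current or a higher dose, with no exception for Arm 1. That conflicts with Section 4.2.
- **Arm 3 is not itself a source of bias.** It is randomised 1:1, so in the atorvastatin split it adds heterogeneity, not imbalance.

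**Conclusion.** The point holds. Objective 4 is a partly observational, two-level comparison presented as a dose-response, and Section 9 does not repair it. About 37% of the maximal side is non-randomised across statins; per-statin shares cannot be derived from the documents.

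The error rates are illustrations, not properties of the plan. They rest on assumed Arm 1 risk ratios, no adjustment and a 14.5% rate inferred from another comparison, and they cover eCD only. A reader might take 24% as the trial's false-positive rate. The documents do not support that: it needs Arm 1 to carry half the risk of the others, and it belongs to a pooled test that Objective 4 does not name. The three per-statin contrasts it does name reach about 10-12% in that case, under an assumed equal split.

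Objectives 1 and 3 remain randomised, so the weakness is confined to Objective 4, whatever Secondary Objective 2 draws from it, and how its result would be described.

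**What to change.** 1. Base Objective 4 inference on randomised patients by assigned group. For each statin, give the raised v current-dose contrast in Arm 2. Give Arm 3 atorvastatin 80 mg v 10 mg separately, or combine the contrasts stratified by arm and statin.
2. Report the all-patient contrast that includes Arm 1 as observational, with a pre-specified covariate set in place of selection at p<0.10.
3. Rename the objective maximal v sub-maximal.
4. Label any analysis by starting or actual dose in mg as exploratory. In Arm 2 the size of the increase is the maximum minus a dose the patient's own doctor chose, so it is not randomised and an interaction with it is not a randomised dose-response.
5. State that patients whose regimen is modified stay in their assigned group.
6. Reconcile the simvastatin-plus-amlodipine definition of maximal (Precis, Sections 3 and 5.1) with the literal 40 mg cut in Section 1.1, and the Arm 1 intolerance exemption in Section 4.2 with Section 7.3.

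**Cost.** The doses and arms needed are already recorded, but changing a primary objective needs a protocol amendment, with a matching check of Secondary Objective 2. Intervals widen: the overall minimum detectable reduction is about 42% instead of 38% at an assumed 16% control rate. Per-statin contrasts will be imprecise; with 113 v 112 in Arm 2, the same formula needs a reduction of about 71% at that rate.

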1.2 Secondary Objectives

- 1) To determine whether a pre-operative statin regimen alters the prevalence of early mortality at Day 365 +/- 30.
- 2) To determine whether differences in eCD/dCD identified in Primary Objectives 1- 4 are associated with either:
 - a. levels of, or peri-operative changes in, ESR/CRP, and/or
 - b. changes in either activities of daily living (BLESSED) or cognition (TICS-M) in the year following randomization and surgery.

2 BACKGROUND AND RATIONALE

2.1 Background on Cognitive Dysfunction, Statins, and CEA

High-grade extra-cranial carotid artery stenosis accounts for nearly 120,000 strokes annually in the USA (3) and many of these patients will undergo CEA surgery. CEA reduces the risk of

future stroke in this patient population by 55-65%, but its effectiveness is dependent on very low peri-operative morbidity. Recent improvements in the medical management of patients with asymptomatic stenosis have improved the outcome for un-operated patients to such a degree that some have even questioned whether the benefits of asymptomatic CEA still justify its risks

[figure not shown]

Figure 1. eCD & Elevations in S100B

cerebral injury to inform treatment decisions, as well as, to improve procedural safety. Several groups have previously used neuropsychological tests to evaluate outcome after CEA (4-9). eCD affects up to 25% of patients undergoing CEA for those that were statin naive. Defined as a worsening in cognitive performance of ≥ 2 standard deviations (SD) on ≥ 2 cognitive domains –

[figure not shown]

Figure 2: Pre-operative statin use is associated with less postop stroke (top) and eCD (bottom), and Simvastatin is associated with less than Atorvastatin (bottom, right)

[figure not shown]
even though the rate of peri-operative stroke has fallen precipitously over the same period to less than 1.5%. While this debate can only be settled by a large, massively expensive, clinical trial like the presently recruiting CREST-II, it is nevertheless critical that perioperative management continue to evolve if the neuroprotective effects of CEA are to be realized for not only asymptomatic, but symptomatic patients as well. Given that post-CEA stroke is so rare, investigators have increasingly looked to subtler forms of

verbal memory, visuo-spatial organization, motor function, and executive action – or ≥ 1.5 SD worse on >4 cognitive domains when compared to a surgical reference group at 24hrs. eCD is associated with marked elevations in tissue markers of cerebral injury (S100B) (10) (Figure 1) and is associated with earlier post-CEA mortality (2, 11, 12). This clinically significant, but occult, cerebral injury is 10 times more common than stroke and its mechanism appears to be similarly related to regional hypoperfusion and ischemia. We now have data that pre-operative statin use is not only associated with a reduction in perioperative clinical stroke, but a 50% reduction in eCD (Figure 2) (72). While no patient taking statins actually suffered a stroke, the rate of eCD varied dramatically among both statin type and dose. In fact, in looking at the incidence of eCD in those taking the two most commonly prescribed agents (80% of

patients),

simvastatin use was associated with significantly less eCD than atorvastatin at any dose (Figure 2) (76). This difference was observed at all doses with the exception of high dose atorvastatin (80mg), which provided similar neuroprotection as simvastatin (40mg). We also observed that statin use was associated with less risk of early mortality (12.5 years vs. 16.0 years; $\chi^2=6.5$, $P=0.01$) that appears to be completely related to its effect on eCD (Figure 3), supporting the contention that statins not only protect against injury, but may be involved in injury repair as has been shown previously in animals.

As >50% of patients are on a sub-optimal statin regimen, it is imperative that we determine in a prospective randomized trial whether alteration of preoperative statin regimens leads to improved neurologic outcome, an even lower incidence of stroke, and possibly greater survival. In order to optimally design and conduct such a trial it is critical that we: 1) explore the safety and feasibility of altering statin regimen acutely (approximately 2 weeks) before CEA, 2) clearly establish the neuroprotective outcome of an acute alteration in statin regimen, and 3) determine if statins that pass the blood-brain barrier more easily are more efficacious. If we can do this, we will be well on our way to achieving our ultimate goal of better understanding statin neuroprotection in humans and determining the optimal statin treatment that affords the most neuroprotection in patients undergoing one of the most commonly performed procedures in the US.

